5.5. Life Style Guidelines

During the study female patients of childbearing potential must take precautions to prevent pregnancy since the effects on the fetus are unknown. Male patients with partners of childbearing potential must take precautions to prevent pregnancy of the partner since the effects of these drugs on sperm are unknown. These restrictions should remain in force for 6 months from the last dose of Axitinib. Drug interaction studies with oral contraceptives have not been performed, so barrier methods of contraception or abstinence should be considered. Adequate contraception should be discussed with the physician before the treatment start.

6. TRIAL PROCEDURES

6.1. Subject Enrollment

Once eligibility is verified the clinical representative will confirm by facsimile that the patient has been accepted into the trial. If the patient fails to start treatment within 14 days of registration the clinical representative should be contacted before the start of treatment.

6.2. Trial procedures

During treatment on this protocol, all patients will be followed and monitored as follows:

Table 6. Trial Procedures.

		Cycle						Following	Following completion	al ¹¹
D 1	D	l,	1		2	4	0	each	of even	viv
Required	Pre-	Day		2	3	4	8	cycle thru	numbered	Sur
studies	therapy ¹²		week	weeks	weeks	weeks	weeks	12 cycles ¹	cycles	01
Clinic visit	X	X		X		X	X	X	X	
H&P	X	X^{10}		Х		X	X	Х	Х	
Vital signs and PS	Х	Х		Х		Х	Х	Х	Х	
PTT, PT, INR	Х									
CBC, Diff, platelets	Х	X ⁹		Х		Х	Х	Х	Х	
Comprehensive Panel, Mg ²	X ³	X ⁹		Х		Х	Х	Х	Х	
Urine dip ³	Х					Х	Х	Х	Х	
TSH, free T4 ⁴	Х	X ^{9,}		Х		Х			Х	
Clinical										
toxicity				Х		Х	Х	Х	Х	
assessment										
Radiologic										
imaging for	v						v		\mathbf{v}	
tumor	Λ						Λ		Λ	
measurement ⁵										
Pregnancy Test ⁶		X ⁹								
Informed	v									
Consent	Λ									
Planned dose				v	v					
escalation ⁷				Λ	Λ					
Telephone										
assessment of			Х		Х					
toxicities ⁸										
Survival										v
Monitoring										Λ

- 1- Following completion of 12 cycles, assessments will be obtained every 8 weeks.
- 2- Comprehensive Panel includes Basic Panel (Na, K, Cl, CO2, BUN, Cr, Gluc), AST/SGOT, ALT/SGPT, Alk Phos, T.bili, Alb, Ca, Total Protein. Also will obtain magnesium.
- 3- Urine dipstick may be done in clinic or lab.
- 4- Serum or plasma Thyroid Function Tests (Free T4 and TSH) should be performed within 14 days of starting treatment. Subsequently, TSH should be done every 2 weeks X 2, then following completion of even numbered cycles of chemotherapy.

- 5- Radiologic imaging of the areas involved with recurrent/metastatic disease, such as the neck, chest, or other areas if needed because of the location of the metastatic disease; baseline within 28 days prior to treatment. On study assessments, may be within +/- 2 weeks. Imaging will be interpreted by Choi Criteria, interpretation to be performed by centralized UMCC Tumor Response and Assessment Core (TRAC).
- 6- Pregnancy test (urine or serum) will be performed for women of childbearing age within 3 days before first dose of Axitinib and if clinical concern for pregnancy arises.
- 7- Dose escalation is planned at 2 weeks (to 7 mg BID) and 3 weeks (to 10 mg BID), in the absence of toxicities grade 2 or greater. Dose escalation may be resumed after 1 week if all toxicities have diminished to grade 1 or less (see below), and measures have been taken to reasonably prevent recurrence of these toxicities with the higher dose.
- 8- Telephone call to the patient must be made by a study staff member (RN or MD with a current nursing/medical license) at 1 and 3 weeks. During these calls, toxicity assessment will be conducted, per patient report, and toxicity management advice given, including initiation or titration of anti-hypertensive treatment. During the Week 3 call, if toxicities are grade 1 or less dose escalation to 10 mg BID will be made.
- 9- All baseline labs are required within 14 days of starting treatment (Cycle 1, Day 1).
- 10-H&P not required on Cycle 1, Day 1 if performed for screening within 72 hours
- 11- Survival assessment can be done by phone and will be performed once every three months (+/- 1 month)
- 12-Labs are eligible for screening if obtained within the past 28 days

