7. STUDY PLAN

7.1. Study overview

The patients will receive 5 mg Axitinib twice a day. Dose escalation is planned at 2 weeks (to 7 mg BID) and at 3 weeks (to 10 mg BID), in the absence of toxicities grade 2 or greater. Dose escalation may be resumed at next visit if all toxicities have diminished to grade 1 or less (see

below) since last follow-up. Each patient will be seen in clinic at 2, 4, 8 weeks after initiation of treatment and at monthly intervals thereafter, unless more frequent follow-up is clinically indicated.

During follow-up visits, we will assess the toxicities, including checking vital signs, review of systems, physical exam and CBCDP, comprehensive metabolic panel, test for proteinuria. TSH should be checked within 14 days of cycle 1, day 1 then should be done every 2 weeks for two assessments. Following completion of these assessments, TSH should be checked following the completion of even numbered cycles of chemotherapy.

Telephone call to the patient must be made by a study staff member (licensed RN or MD) at 1 and 3 weeks. During these calls, toxicity assessment will be conducted, per patient report, and toxicity management advice given, including initiation or titration of anti-hypertensive treatment. During the Week 3 call, if toxicities are grade 1 or less since last follow-up, dose escalation to 10 mg BID will be made. Dose escalation may be resumed at least 1 week later if all toxicities have diminished to grade 1 or less (see below), and measures have been taken to reasonably prevent recurrence of these toxicities with the higher dose since last follow-up.

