8.2.3. Dose escalations

Dose escalation is planned at 2 weeks (to 7 mg BID) and at 3 weeks (to 10 mg BID), in the absence of toxicities grade 2 or greater since last follow-up. Dose escalation may be resumed after at least 1 week if all toxicities have diminished to grade 1 or less since last follow-up. Each patient will be seen in clinic at 2, 4, 8 weeks after initiation of treatment and at monthly intervals thereafter, unless more frequent follow-up is clinically indicated. Telephone call to the patient must be made by a study staff member (a doctor or a nurse) at 1 and 3 weeks, +/- 3 days. During these calls, toxicity assessment will be conducted, per patient report, and toxicity management advice given. During the Week 3 call, if toxicities are grade 1 or less since last follow-up, Axitinib dose escalation to 10 mg BID will be made. Dose escalation up to 10 mg po BID may be resumed after at least 1 week if all toxicities have diminished to grade 1 or less (see below), and measures have been taken to reasonably prevent recurrence of these toxicities with the higher dose. The contents of each planned and patient-initiated phone called will be recorded in patient's study record.

If a patient has a dose reduction for study drug related toxicity, the dose may be considered for re-escalation in patients who tolerate the lower dose without toxicities above Grade 1 for at least 1 week, and measures have been taken to reasonably prevent recurrence of these toxicities with the higher dose.

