8.2.4. Dose Interruption and Reductions

Adverse events and other symptoms will be graded according to the current Common Terminology for Adverse Events version 4.03 (CTCAE v4.03). This section contains management of adverse events except hypertension, hemoptysis and proteinuria which are discussed in subsequent sections.

Patients developing a treatment-related CTCAE Grade 1 or 2 adverse event will have their dose continued at the same dose level. Patients developing a treatment-related CTCAE Grade 3 or above adverse event will have dose reductions as described below.

Treatment delays due to drug-related toxicity > 2 weeks will result in discontinuation of treatment. Patients removed from treatment for intolerable toxicity will still be followed for survival.

The criteria for dose modification for study drug related adverse events is summarized Table 8 below.

Table 8. Criteria for Dose Modification for Axitinib Related Adverse Events other than Hypertension, Hemoptysis, or Proteinuria

Related Adverse Events	Intervention
Grade 1	Continue at same dose level
	May escalate dose per protocol
	Manage toxicities as medically necessary
Grade 2	Continue at same dose level
	Manage toxicities as medically necessary
Grade 3 nonhematologic	Decrease dose to one lower dose level
drug-related toxicity	Manage toxicities as medically necessary
	Treatment may be interrupted up to 2 weeks per investigator discretion
Grade 4 nonhematologic drug-related toxicity or Grade 4 hematologic toxicity*	Interrupt dosing (up to 2 weeks); re-start at one lower dose level as soon as improvement to CTCAE Grade 2. If patient requires dose reduction below 2 mg BID, discontinue trial participation. Manage toxicities as medically necessary
*Patients who develop grade 4 lymphopenia may continue study treatment without interruption.	

Guidelines for dose reductions for specific adverse events are provided in the following sections.

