8.2.4.1. Axitinib Dose Reduction for Hypertension

Patients treated with Axitinib will monitored for hypertension closely in the office. Blood pressure will be monitored closely at routine visits. If hypertension is noted at the time of the initial encounter, it will be checked 5 minutes after sitting quietly.

Guidance on dose interruption and reduction for hypertension is summarized in Table 9 below. If "white coat hypertension" is suspected by the clinician same anti-hypertensive regimen and dose of Axitinib can be continued.

Table 9. Hypertension Management Plan for Axitinib

Degree of Blood Pressure Elevation	Management
2 BP readings separated by at least 30 min show systolic pressure 141-160 mm Hg OR diastolic pressure 91-100 mm Hg	If not on maximal antihypertensive treatment, institute new or additional antihypertensive medication and maintain dose of study drug. If on maximal antihypertensive treatment (3 agents including a diuretic, and no further safe and efficacious escalation of antihypertensive therapy is deemed possible by the investigators), reduce study drug to one lower dose level.
2 BP readings separated by at least 30 min show systolic Pressure 161 or above OR diastolic pressure 101 or above	Interrupt dosing; adjust antihypertensive medication; as soon as BP is 140/90 mm Hg or less, restart study drug at one lower dose level.
Recurrent hypertension following previous dose reduction (2 BP readings separated by at least 30 min show systolic pressure 141-160 mm Hg OR diastolic pressure 91- 100 mm Hg	Repeat study drug dose reduction by one lower dose level. If a patient requires dose reduction below 2 mg BID, take off study.
Hypertensive urgency or emergency while on study drug, with any blood pressure level above 140/90	Take patient off study immediately. Manage as medically appropriate, in the appropriate hospital setting.

If study drug is held, patients receiving antihypertensive medications should monitor closely for hypotension. Plasma half-life of Axitinib is 2-4 hours and BP usually decreases within 1-2 days following dose interruption.

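### The step from 7 to 10 mg BID is made on the week-3 telephone call, with no blood pressure reading required on 7 mg BID

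*Combined protocol and SAP*

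**What the plan says.** Section 6.2, Table 6 footnote 7 plans escalation to 7 mg BID at week 2 and to 10 mg BID at week 3, provided there is no toxicity of grade 2 or worse. Footnote 8 makes the second step part of a telephone call: "During the Week 3 call, if toxicities are grade 1 or less dose escalation to 10 mg BID will be made". Sections 7.1 and 8.2.3 repeat the rule, and all three places base the toxicity assessment on the call on the patient's own report. Section 8.2.3 places the calls "at 1 and 3 weeks, +/- 3 days".

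Section 7.1 sets the clinic schedule: "Each patient will be seen in clinic at 2, 4, 8 weeks after initiation of treatment". Table 6 marks vital signs at weeks 2, 4 and 8. At week 3 it marks only the telephone assessment and the planned escalation. Section 8.2.4.1 ties hypertension monitoring to the office: "Blood pressure will be monitored closely at routine visits".

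The call may also be used to treat hypertension. Footnote 8 describes "toxicity management advice given, including initiation or titration of anti-hypertensive treatment", and 7.1 says the same. No section says where a blood pressure value for the call would come from.

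**The concern.** The condition for escalating is a toxicity grade, and 8.2.4 has adverse events graded by CTCAE v4.03, so hypertension is nominally covered. But a patient with raised pressure and no symptoms has nothing to report. Without a measurement on the current dose, the condition cannot be applied to the toxicity that most needs it.

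The stake is patient safety in the first month. Table 9 calls for new or additional antihypertensive treatment (or a dose reduction if treatment is already maximal) at 141-160 systolic or 91-100 diastolic, and for interruption at 161 or 101 and above. A patient in either range on 7 mg BID could be moved to 10 mg BID with every written step followed.

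**Working it through.** **Which reading covers which dose.** The plan gives no figure for this, so the check sets the schedule against the dose steps.

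| Time | Contact | Required BP reading | Dose at the time | Planned step |
|---|---|---|---|---|
| Week 2 | Clinic | Yes | 5 mg BID | to 7 mg BID |
| Week 3 | Telephone | No | 7 mg BID | to 10 mg BID |
| Week 4 | Clinic | Yes | 10 mg BID | none planned |

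No required reading falls on 7 mg BID.

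**Length of the gap.** Inputs: visits taken as days 14 and 28 (an assumption; the text gives weeks), and the call at day 21 with the 3-day window of 8.2.3.

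- Call window: 21 - 3 = day 18 to 21 + 3 = day 24.
- Days on 7 mg BID before the step: 18 - 14 = 4 to 24 - 14 = 10.
- Days on 10 mg BID before the week-4 reading: 28 - 24 = 4 to 28 - 18 = 10.
- Between the two required readings: 28 - 14 = 14 days, containing both planned dose increases.

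**Size of the step.** From 2 × 7 = 14 to 2 × 10 = 20 mg/day: 6/14 = 42.9%, about 43% more drug. This is a dose ratio, not a measure of harm.

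**How common the toxicity is.** Table 2 (N = 515, single-agent axitinib, all-causality) gives grade 3 or worse hypertension as 92/515 = 17.9%, which reproduces. The next most frequent grade 3 or worse event is fatigue, 56/515 = 10.9%. These rates cover whole treatment. They are not rates for the days on 7 mg BID.

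**How earlier studies escalated.** Section 1.1.2 describes stepwise increases after 2-week periods of tolerance, not allowed if pressure was above 150/90 mm Hg or the subject was on antihypertensive medication. The escalation rule in this protocol has no blood pressure condition of that kind.

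**The case against.** The strongest reply is that this is an unwritten operational detail. Section 1.2 mentions home blood pressure readings when reporting the earlier trial and describes the treatment plan here as the same apart from the response criteria. Letting staff adjust antihypertensives by telephone suggests that a value is expected to be at hand. Home readings may well be used in practice. What stands against this is that the current protocol nowhere requires them, and the earlier protocol is not in the documents.

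Several mitigating facts also stand. Section 1.1.2 reports only a small rise in hypertension among patients titrated to 6-10 mg BID who had tolerated 5 mg BID, although most of those studies applied a blood pressure condition. The earlier trial was well tolerated, with no dose reductions prompted by home readings. Entry requires readings of 140/90 mm Hg or less, extra visits are allowed when clinically indicated, and 8.2.4.1 notes that pressure usually falls within 1-2 days of interruption. A delayed escalation may fall at a clinic visit, where vital signs are taken. These limit the exposure, but none supplies a required reading before the on-schedule week-3 step.

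A reader might infer that the escalation rule ignores hypertension. It does not, because the grade condition includes it. Nor can it be said that the rule lacks numeric limits altogether, since that depends on the CTCAE text, which the documents do not reproduce. What is missing is the measurement needed to apply the grade.

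**Conclusion.** The gap is real and should be closed. On the planned schedule, the step to 10 mg BID rests on patient report, with no required blood pressure reading on 7 mg BID. Under the assumed visit days, a patient who takes the step on time spends 4 to 10 days on 7 mg BID unmeasured, then another 4 to 10 days on 10 mg BID before the next required reading.

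Two stronger readings are not supported. Multiplying 17.9% by the 37 planned patients would not give the number escalated while hypertensive, because the rate covers whole treatment. And 37 is planned enrolment, not the number who take the week-3 step: patients with toxicity of grade 2 or worse do not step on schedule. Neither the number taking the step nor the number hypertensive at that point can be derived from the documents.

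This is a safety point only. The sample size, type I error, power and primary analysis are unaffected.

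**What to change.** Add to Table 6 footnotes 7 and 8, and to 7.1 and 8.2.3:

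> Before any escalation made by telephone, including the week-3 step, a blood pressure reading (home, local or clinic) taken on the current dose must be recorded. If it is above 140/90 mm Hg, repeat after at least 30 minutes. Escalate only if blood pressure is 140/90 mm Hg or less; otherwise do not escalate, and manage per 8.2.4.1 and Table 9. If no reading is available, defer escalation until there is one.

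The 140/90 limit is stricter than the 150/90 described for earlier studies. It is chosen because it is already this protocol's entry limit (5.2, item 7) and the Table 9 restart limit, and Table 9 calls for action from 141 systolic or 91 diastolic.

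There should be no white-coat exception for escalation. Where white-coat hypertension "is suspected by the clinician same anti-hypertensive regimen and dose of Axitinib can be continued", which permits staying on the same dose but not raising it.

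The cost is wording in three places, one or two extra readings per patient, a home cuff or local check for some, and a short delay in escalation for some. If home readings are already routine, the change only writes the practice down.

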3.2 Secondary objectives

- 1. To determine the overall survival of patients treated with Axitinib
- 2. To determine the progression free survival of patients treated with Axitinib
- 3. To determine the disease control rate at 16 weeks and response rate as defined by Choi Criteria
- 4. To determine the duration of response (as defined by Choi Criteria) of patients treated with Axitinib
- 5. To assess the toxicities associated with the treatment of Axitinib of patients treated with Axitinib

4. STUDY DESIGN:

This study will be a prospective, single-institution, single-arm phase II study of Axitinib in patients with unresectable recurrent and metastatic head and neck squamous cell carcinoma with ECOG performance status 0-2, for recurrent or metastatic head and neck cancer. The subjects will be started on treatment with 5 mg of Axitinib twice a day continuously, with subsequent dose escalation to 7 mg and then 10 mg twice a day in the absence of grade 2 or worse toxicities. This will be followed by clinical and/or radiologic response assessment after 8 weeks and subsequently every 2 months until disease progression (defined per Choi criteria, or obvious progression on clinical or laryngoscopic/endoscopic exam) or intolerable toxicity (defined as below). Patients with confirmed progressive disease who, in the investigator's opinion, continue to receive benefit from Axitinib treatment and who meet the criteria for treatment may continue to receive treatment as described in Section 8.3. Axitinib should be discontinued if there is further evidence of progression defined as an additional 10% or greater increase in tumor burden volume from time of initial progression (including all target lesions and new measurable lesions).

During treatment on this protocol, all patients will be evaluated for safety as detailed below.

5. STUDY POPULATION:

5.1. Stage:

Unresectable, recurrent or metastatic squamous cell carcinoma of head and neck.

5.2. Inclusion Criteria:

1. Histologically documented squamous cell head and neck cancer with or without metastases, not amenable to curative treatment; or the patient has documented refusal of curative treatment.

2. Presence of measurable disease by CT scan or

a. for cutaneous squamous cell carcinoma not present on CT imaging but present on physical exam with lesion(s) greater than >/= 10mm

b. patients with non-target lesions are permissible per PI discretion

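### The Week 3 call rule raises the dose to 10 mg BID without requiring that the patient be on 7 mg BID; read literally, it doubles the dose of some patients held at 5 mg BID

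*Combined protocol and SAP*

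**What the plan says.** Section 4 sets the order of the steps: "with subsequent dose escalation to 7 mg and then 10 mg twice a day in the absence of grade 2 or worse toxicities". Table 6 footnote 7, Section 7.1 and Section 8.2.3 attach the 7 mg step to week 2 and the 10 mg step to week 3. Table 7 lists 7 mg BID as a level of its own between 5 and 10 mg BID.

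The Week 3 call has its own sentence in three places:

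- Table 6 footnote 8: "During the Week 3 call, if toxicities are grade 1 or less dose escalation to 10 mg BID will be made".
- Section 7.1: "if toxicities are grade 1 or less since last follow-up, dose escalation to 10 mg BID will be made".
- Section 8.2.3: "if toxicities are grade 1 or less since last follow-up, Axitinib dose escalation to 10 mg BID will be made".

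A patient with a related grade 2 event is not escalated. Section 8.2.4 says: "Patients developing a treatment-related CTCAE Grade 1 or 2 adverse event will have their dose continued at the same dose level". Separate sentences govern taking up escalation again. Footnote 7 says: "Dose escalation may be resumed after 1 week if all toxicities have diminished to grade 1 or less". Section 8.2.3 says: "Dose escalation up to 10 mg po BID may be resumed after at least 1 week". The opening paragraph of 7.1 instead ties resumption to the next visit. Footnote 7 and the later statements in 7.1 and 8.2.3 also require steps to prevent the toxicity from recurring.

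**The concern.** The Week 3 sentence looks at toxicity grade and not at current dose. It was evidently written for a patient who moved to 7 mg BID at week 2. It applies just as well, word for word, to one who did not. For that patient the named target skips a level.

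The step is taken by telephone, on toxicity as the patient reports it, by any licensed nurse or doctor on the study staff. Table 6 schedules vital signs and laboratory tests at weeks 2 and 4, not at the Week 3 call. Hypertension is the most frequent grade 3 or worse event in Table 2 (92 of 515 subjects, 17.9%). The Week 3 sentence also lacks the preventive-measures condition. A double step could therefore be made with fewer conditions than a resumption, in a patient whose previous step was withheld for toxicity at 5 mg BID. What is at stake is dosing safety and uniform conduct, not the primary analysis.

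**Working it through.** The plan states no figure on this point. The check is a comparison of texts, followed by dose arithmetic.

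**1. What each statement fixes**

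| Place | Toxicity condition | Current dose required | Next dose named |
|---|---|---|---|
| Section 4 | no grade 2 or worse | order 5, 7, 10 | 7, then 10 mg BID |
| Footnote 8, Week 3 call | grade 1 or less | none | 10 mg BID |
| 7.1 and 8.2.3, Week 3 call | grade 1 or less since last follow-up | none | 10 mg BID |
| Footnote 7, resumption | all grade 1 or less, after 1 week, prevention in place | none | none |
| 7.1 opening, resumption | all grade 1 or less, at next visit | none | none |
| 8.2.3 (later statement), resumption | all grade 1 or less, after at least 1 week, prevention in place | none | a ceiling of 10 mg BID only |

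Reductions, by contrast, are expressly by one level (Tables 8 and 9, Section 8.2.4.3). The protocol states single-level steps downward but not upward.

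**2. Which held patients meet the Week 3 sentence**

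Take the week 2 visit as the last follow-up before the call.

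- Patient A had a grade 2 event between the week 1 call and the week 2 visit, and it had settled by that visit. Section 8.2.3 judges the week 2 step on toxicity since last follow-up, so A is held at 5 mg BID. If A stays at grade 1 or less until the call, all three Week 3 sentences are met and name 10 mg BID.
- Patient B had a grade 2 event that persisted after the week 2 visit and settled before the call. B fails the condition in 7.1 and 8.2.3, because there was grade 2 toxicity since last follow-up. B meets footnote 8, which omits that phrase.

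Patients whose dose was reduced have their own paragraph in 8.2.3 and are not part of this point.

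**3. Size of the step** (doses from Table 7)

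- Literal step: 10/5 - 1 = 100%.
- Planned first step: 7/5 - 1 = 40%.
- Planned second step: 10/7 - 1 = 42.9%.
- Daily dose: 2 x 10 = 20 mg on the literal reading; 2 x 7 = 14 mg on the stepwise reading.
- If the stepwise route reaches 10 mg BID one week later: 20 x 7 = 140 mg against 14 x 7 = 98 mg. The difference is 42 mg, or 140/98 - 1 = 43%, over that week.

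**4. Timing under a one-level rule**

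Assume the week 2 visit falls on day 14 and the resumption week is counted from that hold. Section 8.2.3 allows 3 days either side of week 3, so the call falls on days 18 to 24, which is 4 to 10 days after the hold.

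- Call on day 21: 7 days have passed and 7 mg BID can start. A further week gives 10 mg BID on day 28, the week 4 visit.
- Call on days 22 to 24: a further week ends on days 29 to 31, after the week 4 visit. The next scheduled clinic visit is week 8.
- Call on days 18 to 20: the week has not passed, so the dose stays at 5 mg BID until a later contact.

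**The case against.** The strongest reply is that the order is already settled. Section 4 puts 7 mg before 10 mg, and its wording is directive too. In 7.1 and 8.2.3 the Week 3 sentence follows the two-step schedule and describes its second step for a patient on track. The resumption sentence comes directly after it and covers patients whose step was withheld. Resuming a 7-then-10 sequence ordinarily means taking the missed step. Section 8.1 also speaks of escalation to 10 mg BID without mentioning 7 mg, which suggests that the phrase is shorthand for the target dose.

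That reading is sensible and is probably what was intended. But no resumption sentence names a dose, and the Week 3 sentence is a direct instruction with one target and no condition on current dose.

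The reply is also right that the consequence is limited. The difference may last one week, at a dose the protocol plans to reach. The week 4 visit, the dose-reduction rules and a plasma half-life of 2-4 hours all limit harm. Assessment by telephone applies to every patient's Week 3 step, not only to held patients. The toxicity bar for escalation is stricter than the one Section 1.1.2 describes for earlier axitinib studies, although those studies stepped through 7 mg BID.

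Two stronger readings do not survive. A reader might infer that the text gives three conflicting doses at the call: 10, 7 or 5 mg BID. Staying at 5 mg BID is not a true conflict: resumption is only permitted, and on an early call the 1-week minimum is simply unmet. A reader might also infer that the only binding wording points to the largest step, but Section 4 is binding as well.

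**Conclusion.** The point holds as a wording defect with a safety consequence. Followed as written, the Week 3 sentence takes a held patient whose grade 2 toxicity has settled from 5 to 10 mg BID in one step, contrary to Section 4. The step is +100% against planned steps of +40% and +43%. The excess over the stepwise route is 42 mg if that route reaches 10 mg BID a week later.

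It would be wrong to infer that every patient held at week 2 is exposed. Under 7.1 and 8.2.3 the path is open mainly to patients whose grade 2 event had settled by about the week 2 visit. Only footnote 8 admits those who settled later. The documents do not say how many patients will be held, so no count is given. Sample size, power and type I error are not affected.

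The result assumes that the last follow-up before the call is the week 2 visit. The timing in the working also assumes a day 14 visit and a resumption week counted from the hold.

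**What to change.** In footnote 8, Section 7.1 and Section 8.2.3, state that the Week 3 call raises the dose by one level only:

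- to 10 mg BID if the patient is on 7 mg BID and toxicities have been grade 1 or less since last follow-up;
- to 7 mg BID if the patient is still on 5 mg BID and the existing resumption conditions are met: at least 1 week since the hold, all toxicities grade 1 or less, and preventive measures taken.

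Add the since-last-follow-up condition to footnote 8, so that the three places agree. In the opening paragraph of 7.1, replace the next-visit rule with the at-least-1-week rule. The call window does not need to change: the 1-week minimum already deals with an early call.

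The cost is protocol wording and no extra patients. Held patients reach 10 mg BID later, at week 4 at the earliest. If the call falls after day 21 and a further week at 7 mg BID is required, the last step needs an unscheduled contact or waits for a later visit. The amendment should say which.
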